This clinical trial (Study GS-US-312-0117) is a separate, multicenter, 2-arm, double-blind, parallel-group extension study that is a companion trial to Study GS-US-312-0116; in this trial, compliant subjects from GS-US-312-0116 who are tolerating primary study therapy but experience definitive CLL progression are eligible to receive active blinded idelalisib therapy at the standard dose or a higher dose, with allocation based on the original primary study randomization. In the event GS-US-312-0116 is stopped early due to overwhelming efficacy following an interim analysis or at the final analysis, subjects who are on Study GS-US-312-0116 at that time may transition to GS-US-312-0117. Additionally, GS-US-312-0117 will become an open-label study offering idelalisib 150 mg BID to GS-US-312-0116 subjects who were randomized to placebo, and subjects randomized to idelalisib will continue idelalisib at 150 mg BID.

Study Schema:

Treatment Groups

Blinded Portion

- Arm A: Idelalisib + rituximab (Study GS-US-312-0116) ⇒high-dose idelalisib (300 mg BID) (Study GS-US-312-0117)
- Arm B: Placebo + rituximab (Study GS-US-312-0116)
 ⇒standard-dose idelalisib (150 mg BID) (Study GS-US-312-0117)

Open-Label Extension Portion (following unblinding)

- Arm A: subjects already on 300 mg BID will continue, and newly enrolled subjects will receive 150 mg BID
- Arm B: subjects already on 150 mg BID will continue, and newly enrolled subjects will receive 150 mg BID

Treatment Assignment

- Assignment to Arm A or Arm B with allocation based on the original primary study randomization
- Implementation through an interactive web response system (IWRS)

Stratification

Not applicable for Study GS-US-312-0117

Number of Subjects Planned:

Total of up to ~180 subjects (up to ~90 subjects per treatment arm)

Target Population:

Subjects in the primary Phase 3 study (GS-US-312-0116) who are compliant, are tolerating primary study therapy, and 1) have definitive progression of CLL while receiving primary study drug therapy (idelalisib/placebo) or 2) are actively participating in Study GS-US-312-0116 at the time the study is stopped, including if stopped early due to overwhelming efficacy following an interim analysis.

Duration of Treatment:

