Clinic/laboratory visits will occur every 2 weeks for the first 12 weeks, every 4 weeks between Weeks 12 and 24, and every 6 weeks between Weeks 24 and 48. Subjects continuing on study drug past Week 48 will have clinic visits every 12 weeks. Subjects will be assessed for safety at each visit. Subjects will be assessed for CLL disease status by physical and laboratory examinations at each visit and by CT or MRI at Weeks 8, 16, 24, 36, and 48 and every 12 weeks thereafter. As of Amendment 9, Version 10, CT/MRI assessments will no longer be performed at the every 12 week scheduled visits, and will only be performed at the time of clinically-suspected disease progression or at study discontinuation.

Following unblinding of the study:

- Subjects who were randomized to idelalisib on Study GS-US-312-0116 and who received ≥ 24 weeks idelalisib will complete Visit 16+ twelve weeks from the date of their last radiology assessment (CT/MRI) and study visits will continue every 12 weeks thereafter. Visits 3 through 15 will not be required.
- Subjects who have received < 24 weeks idelalisib will have all Study GS-US-312-0117 assessments completed per the Schedule of Procedures until they have received idelalisib for 24 weeks cumulative across both studies. After completion of 24 weeks of cumulative idelalisib treatment, Visit 16+ will be conducted 12 weeks from the date of their last radiology assessment (CT/MRI), after which time study visits will occur every 12 weeks.

Test Therapy, Dose, and Mode of Administration:

Blinded Portion

- Arm A: Idelalisib, 300 mg/dose BID starting on Day 1 and administered continuously thereafter; the study drug will be provided as 2 tablets of active idelalisib for oral administration
- Arm B: Idelalisib, 150 mg/dose BID starting on Day 1 and administered continuously thereafter; the study drug will be provided as 1 tablet of active idelalisib and 1 tablet of placebo for oral administration

Open-Label Extension Portion (following unblinding)

- Arm A: subjects already on 300 mg BID will continue, and newly enrolled subjects will receive 150 mg BID
- Arm B: subjects already on 150 mg BID will continue, and newly enrolled subjects will receive 150 mg BID

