Compliant subjects who are tolerating therapy but who develop definitive disease progression in the primary clinical trial (Study GS-US-312-0116) can consider enrollment in this separate companion extension trial (Study GS-US-312-0117). In the extension trial, subjects will take active blinded idelalisib therapy, either at a higher starting dose or at the standard starting dose, with allocation based on the original primary study randomization. Following unblinding of Study GS-US-312-0116, subjects will be allowed to enter Study GS-US-312-0117 in the absence of evidence of disease progression and will take 150 mg BID idelalisib regardless of treatment assignment in Study GS-US-312-0116.

The primary objective of Study GS-US-312-0116 will be to evaluate the effect of the addition of idelalisib to rituximab on PFS. Secondary and tertiary objectives will focus on determining the effect of the addition of idelalisib to rituximab on the onset, magnitude, and duration of tumor control; overall survival (OS); health-related quality of life (HRQL); changes in subject performance status; disease-associated biomarkers and potential mechanisms of resistance; treatment administration; safety; and health resource utilization. In Study GS-US-312-0117, the same endpoints will be assessed as in Study GS-US-312-0116; the focus of the analysis will be largely descriptive except for the within-subject assessment of treatment effects among subjects receiving first rituximab alone and then idelalisib alone on Arm B of each trial. No formal comparisons of outcomes in Arm A vs Arm B are planned within Study GS-US-312-0117.

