2.2. Design Rationale

The randomized, add-on design for the primary trial (Study GS-US-312-0116) is customary in the comparative evaluation of new therapies for cancer. While this design provides idelalisib efficacy and safety information only in the context of administration of a companion antineoplastic agent, it is appropriate because it documents the incremental benefit and toxicity of the investigational therapy in the context of a controlled clinical trial while ensuring that all participants receive potentially active treatment.

This separate extension trial (Study GS-US-312-0117) enhances subject acceptance of randomization in the primary study and provides further information regarding idelalisib efficacy, resistance, and safety. Among subjects in Arm A, escalation to a higher dose level allows evaluation of dose-dependent resistance and a determination if a higher dose can reestablish disease control. The safety data obtained in these subjects will add to the overall safety database. Among subjects randomized to Arm B in the primary study, evaluation of idelalisib at a starting dose of 150 mg/dose BID in the extension study may permit a within-subject assessment of the treatment effects with single-agent idelalisib relative to the effects previously observed with rituximab alone. Of importance, the extension study maintains

the partial blinding of the primary study, thus minimizing the bias that might occur if the overall design entailed only a 1-way crossover to open-label idelalisib among subjects who had received placebo on Arm B of the primary study. To ensure confirmation of disease progression, tumor size data collected from the primary study will be subjected to independent review by an independent review committee (IRC) (see Section 10.4.2); subjects will continue with study therapy pending confirmation of progression status by the sponsor working in collaboration with the IRC. Subjects must have confirmation that the disease has progressed on the primary study before being permitted to receive secondary idelalisib therapy on the extension study, or in the event the primary study is stopped, subjects who have not yet progressed may enroll on the extension study to receive 150 mg BID idelalisib.

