5.3.4. Dose Levels

Study drug dose levels for Arm A and Arm B are described in Table 5-1. The lower dose level (Dose Level -1) is provided in case a subject requires a study drug dose modification.

Table 5-1. Study Drug Dose Levels

Treatment Arm	Starting Dose	Dose Level -1
Arm A	300 mg/dose BID	200 mg/dose BID
Arm B	150 mg/dose BID	100 mg/dose BID

Abbreviation: BID=twice per day

When the primary study (GS-US-312-0116) is stopped, and GS-US-312-0116 active study subjects become eligible for participation on Study GS-US-312-0117 subjects will be enrolled into Study GS-US-312-0117 at open label 150 mg BID. Subjects already participating in Study GS-US-312-0117 will remain on the same dose.

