9.3.2.3. Open-Label Extension Study Analyses

GS-US-312-0117 will become an open-label study offering idelalisib 150 mg BID to GS-US-312-0116 subjects who were randomized to Arm B. Subjects randomized to Arm A will continue idelalisib at 150 mg BID. Efficacy and safety data collected during the primary and open-label extension studies will be presented in the following 4 groups:

- IDELA 150 mg BID: Subjects who are randomized to Arm A in Study GS-US-312-0116 and transition to Study GS-US-312-0117 during the open-label portion of the study to continue IDELA 150 mg BID
- Placebo in GS-US-312-0116 + IDELA 150 mg BID (open-label): Subjects who are randomized to Arm B in Study GS-US-312-0116 and transition to receive IDELA 150 mg BID during the open-label portion of the study
- IDELA 300 mg BID: Subjects who have PD per IRC confirmation in Arm A of Study GS-US-312-0116 and subsequently enroll Study GSUS-312-0117 to receive IDELA 300 mg BID during double-blind portion of the study
- Placebo in GS-US-312-0116 + IDELA 150 mg BID in GS-US-312-0117: Subjects who have PD per IRC confirmation in Arm B of Study GS-US-312-0116 and subsequently enroll Study GS-US-312-0117 to receive IDELA 150 mg BID during double-blind portion of the study.

Depending on the endpoints, analyses may be based on the combined data from both primary and extension studies or data from the extension study alone. Analyses will be descriptive in nature and formal comparisons of outcomes in the 4 groups are not planned. A separate statistical analysis plan will be created for the open-label portion of the study.

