3.5.1. Data Handling for Treatment Groups

Subjects who developed disease progression, confirmed by independent review committee (IRC), in Study GS-US-312-0116 could consider participation in Study GS-US-312-0117. Upon enrollment, subjects who were randomized into Arm A received IDELA 300 mg BID and those who were randomized into Arm B received IDELA 150 mg BID.

Study GS-US-312-0116 was stopped early due to overwhelming efficacy based on results from the first interim analysis and the primary study was unblinded. Under the protocol amendment, all remaining subjects were given the opportunity to enroll in Study GS-US-312-0117 and received IDELA 150 mg BID. The dose increase to IDELA 300 mg BID after confirmed PD on Arm A was no longer offered.

For disposition data summaries, subjects will be assigned into 1 of the following 4 treatment groups:

- IDELA 150 mg BID in GS-US-312-0116 and GS-US-312-0117:
 - Includes all subjects who are randomized to Arm A in Study GS-US-312-0116 except for those who take IDELA 300 mg BID in Study GS-US-312-0117
 - Referred to 'IDELA+R/IDELA' throughout this SAP and the tables, figures, and listings (TFLs)
 - Baseline for efficacy endpoints will be the date of randomization in Study GS-US-312-0116.
 - Baseline for safety endpoints will be the first dosing of IDELA in Study GS-US-312-0116.
 - In the analysis, the Study GS-US-312-0117 portion will include all the data collected on or after the enrollment date of Study GS-US-312-0117.
- IDELA 150 mg BID in GS-US-312-0116 + IDELA 300 mg BID in GS-US-312-0117:
 - Includes subjects who experience IRC confirmed progressive disease (PD) in Arm A of Study GS-US-312-0116 and subsequently enroll into Study GS-US-312-0117 to receive IDELA 300 mg BID during the double-blind portion of the study
 - Referred to 'IDELA+R (PD)/IDELA' throughout this SAP and the TFLs

- Baseline for efficacy and safety endpoints will be the first dosing of IDELA 300 mg BID, unless otherwise specified.
- In the analysis, the Study GS-US-312-0117 portion will include all the data collected on or after the enrollment date of Study GS-US-312-0117.
- Placebo in GS-US-312-0116 + IDELA 150 mg BID (open-label):
 - Includes subjects who are randomized to Arm B in Study GS-US-312-0116 and transition to receive IDELA 150 mg BID during the open-label portion of the study
 - Referred to 'Placebo+R/IDELA' throughout this SAP and the TFLs

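### Table 5-1 has no row for former Arm A subjects who enter the open-label portion at 150 mg BID: the only Arm A Dose Level -1 (200 mg BID) is above their dose, and the Arm A starting dose (300 mg BID) is twice it

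*Protocol*

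**What the plan says.** Table 5-1 in Protocol 5.3.4 has two rows. Arm A starts at 300 mg BID with Dose Level -1 at 200 mg BID. Arm B starts at 150 mg BID with Dose Level -1 at 100 mg BID. The text below the table covers the stop of Study 0116: "subjects will be enrolled into Study GS-US-312-0117 at open label 150 mg BID". The next sentence adds that "Subjects already participating in Study GS-US-312-0117 will remain on the same dose".

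Section 5.1.2 and the synopsis list the open-label groups under the same arm labels. For Arm A and Arm B alike, "newly enrolled subjects will receive 150 mg BID". The dose is repeated elsewhere:

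- Synopsis, study design: "subjects randomized to idelalisib will continue idelalisib at 150 mg BID"
- Section 2.1: subjects "will take 150 mg BID idelalisib regardless of treatment assignment in Study GS-US-312-0116"
- Section 2.2: "subjects who have not yet progressed may enroll on the extension study to receive 150 mg BID idelalisib"
- Section 9.3.2.3: "Subjects randomized to Arm A will continue idelalisib at 150 mg BID"
- SAP 3.5.1: "all remaining subjects were given the opportunity to enroll in Study GS-US-312-0117 and received IDELA 150 mg BID". It adds that the step up to 300 mg BID after progression on Arm A was withdrawn.

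Three other sections depend on Table 5-1. Section 5.3.6 sends dose changes to Tables 5-1 and 5-2. It permits a return to the Table 5-1 starting level once the lower dose has been tolerated for at least 4 weeks and the investigator so decides, and says that level should not intentionally be exceeded. Table 5-2 makes a lower dose level mandatory if drug is restarted after a Grade 4 hepatic event with bilirubin below Grade 4. Section 5.8 ties discontinuation to failure of a second rechallenge at Dose Level -1.

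On supply, 5.2.1 mentions only 150 mg tablets for the open-label portion, while 5.2.3 lists open-label bottles of 150 mg and 100 mg.

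**The concern.** Table 5-1 was built for the blinded portion, where Arm A meant 300 mg BID. The open-label portion added subjects who carry the Arm A label but take 150 mg BID, and the table was not extended to them. For such a subject, the level a site finds by following the label is not a reduction at all.

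These levels are used when a subject has had toxicity. They decide the dose after an interruption, how far the dose may be raised again, and when the drug must be stopped for intolerance. Section 5.8 lets treatment continue indefinitely, so the rule stays in use for any such subject still on drug, even if no one else will transfer.

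A second gap concerns the transfer itself. Section 5.3.4 preserves the current dose only for subjects already in Study 0117. Section 6.2.2 lets drug holds from Study 0116 continue but is silent on reduced doses. The plan therefore does not say at what dose a former Arm A subject on a toxicity reduction should enter.

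**Working it through.** There is no plan figure to reproduce. The check sets the rows of Table 5-1 against the dose each group takes.

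| Group | Dose on entry to 0117 | Row its label points to | Dose Level -1 in that row | Starting level in that row |
|---|---|---|---|---|
| Blinded Arm A | 300 mg BID (5.1.2) | Arm A | 200 mg BID | 300 mg BID |
| Blinded Arm B | 150 mg BID (5.1.2) | Arm B | 100 mg BID | 150 mg BID |
| Open-label newcomer, former Arm B | 150 mg BID (5.3.4) | Arm B | 100 mg BID | 150 mg BID |
| Open-label newcomer, former Arm A | 150 mg BID (5.3.4) | Arm A | 200 mg BID | 300 mg BID |

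The first three lines are coherent. The fourth is not.

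**Dose Level -1, fourth line.** Entry dose: 2 × 150 = 300 mg/day. Arm A Dose Level -1: 2 × 200 = 400 mg/day. Difference: 400 − 300 = +100 mg/day; 200/150 − 1 = +33%. The Arm B value gives 2 × 100 = 200 mg/day; 100/150 − 1 = −33%, a true reduction.

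**Starting level, fourth line.** Arm A row: 2 × 300 = 600 mg/day; 600/300 = 2 times the entry dose.

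**Who the Arm A row fits.** SAP 3.5.1 gives N = 4 for the group that took 300 mg BID after progression. The row describes those four and no Arm A subject who entered at 150 mg BID. The number of former Arm A subjects in the open-label portion is not stated; SAP 1.3 gives only a total of 161 enrolled.

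**Other text on the reduced dose.** Section 5.4.4 says dosing after Grade 4 neutropenia may resume at 100 mg BID, which agrees with the Arm B row. The open-label 100 mg bottles in 5.2.3 point the same way. Section 5.2.1, read alone, names no tablet for a dose below 150 mg.

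**Transfer on a reduced dose.** Assume a reduced Study 0116 dose of 100 mg BID. That protocol is not available; the value is inferred from the Arm B row and from 5.10, which speaks of subjects tolerating at least 100 mg BID. Entering such a subject at 150 mg BID would move 200 to 300 mg/day, 150/100 − 1 = +50%. Section 5.3.6 allows that step only after at least 4 weeks tolerated and by the investigator's choice. The two provisions would conflict only for subjects reduced for less than 4 weeks, or whose investigator would not re-escalate.

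**The case against.** The strongest reply is that no sensible site would misread this. The 150 mg BID entry dose stands directly under Table 5-1 and again in 5.1.2, so it is the natural starting dose for a newcomer. Section 5.3.6 forbids intentionally going above the starting dose, and SAP 3.5.1 confirms that 300 mg BID had been withdrawn. A reader who sees that 200 mg BID is no reduction from 150 mg BID will turn to the 150/100 row. The 100 mg bottles exist, the interactive web response system gives dispensing details at each titration, and dose changes should be discussed with the medical monitor whenever possible.

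Most of this stands as an account of likely practice. It does not remove the defect: the reader reaches the right dose only by setting aside the row that the label selects, and no sentence says to do so. The ban on exceeding the starting dose does not settle the matter either, because 5.3.6 takes that dose from Table 5-1.

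A reader might also infer that 5.3.4 forces a 50% increase on every former Arm A subject who transfers on a toxicity reduction. The text does not clearly support that. The synopsis and 9.3.2.3 say these subjects continue at 150 mg BID, which reads as the assigned dose and describes no increase. The rule for subjects already in Study 0117 can be read as separating 300 from 150 mg BID. Nothing suspends 5.3.6 at transfer, and entry requires the investigator to judge benefit and risk acceptable. What remains is silence on reduced doses.

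**Conclusion.** The point holds as a defect in the dosing table. Read literally, the Arm A row gives former Arm A open-label subjects a Dose Level -1 that is 33% above their dose and a starting level twice their dose. Both are nominal doses. Section 1.3.5.2.1 reports less than dose-proportional exposure, with modest increases above 150 mg BID, so the exposure differences should be smaller. Former placebo subjects are not affected, because the Arm B row fits them.

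Three stronger readings should not be drawn:

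- That 300 mg BID is the operative ceiling for these subjects. The 150 mg BID stated under the table and SAP 3.5.1 both speak against it.
- That transfer imposes an increase on reduced subjects. The wording permits that reading but does not require it. The 100 mg BID level in Study 0116 is inferred, the number on a reduction at transfer is unknown and may be zero, and transfers appear largely complete (161 enrolled; SAP 3.5.1 in the past tense; entry within 12 weeks of Study 0116 participation).
- That results are distorted. Dose reductions and re-escalations are summarised under SAP 4.3.1, and dosing and modification records are listed, so a dose step would be visible.

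The conclusion rests on one assumption: that sites use the arm label in 5.1.2 to find the row in Table 5-1. The documents give them no other key. The correction is worth making because the table governs dosing after toxicity and the change costs almost nothing.

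**What to change.** 1. Add a third row to Table 5-1: subjects newly enrolled in the open-label portion, from either Study 0116 arm; starting dose 150 mg BID; Dose Level -1 100 mg BID. This corrects the references from 5.3.6, Table 5-2 and 5.8 without touching those sections. If only one change is made, it should be this one.
2. Add 100 mg tablets to the open-label sentence in 5.2.1, to match 5.2.3.
3. As a secondary safeguard, state in 5.3.4 that a transferring subject on a toxicity-reduced Study 0116 dose enters at that dose, with any increase only under 5.3.6. If this is adopted, the other statements of the entry dose (synopsis, 2.1, 2.2, 5.1.2 and 9.3.2.3) should refer to 5.3.4 so that no new inconsistency arises.

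Items 1 and 2 cost one table row and one phrase. They need no new supply, since 100 mg bottles are already provided and the interactive web response system already handles titration; its settings for these subjects should be checked against the new row. Item 3 may help few or no further subjects. No change to the SAP is required.

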5.3.5. Dose Schedule Interruptions and Vomited Doses

Subjects who have a delay in administration of a dose of the study drug of <6 hours should take the planned dose as soon as possible after the intended time of administration. For subjects who have a delay in administration of study drug of ≥ 6 hours, the dose should not be taken. Study drug administration may continue but the missed dose should not be made up and the planned timing of subsequent study drug dosing should not be altered.

Vomited doses may be retaken, but only if the tablet is visible in the vomitus.

5.3.6. Safety Monitoring and Study Drug Interruption/Dose Modification

Subjects must be monitored closely for adverse events or laboratory abnormalities during the course of the study. Reference should be made to the CTCAE, Version 4.03 for grading the severity of adverse events and laboratory abnormalities.

Recommendations and requirements for modifications of the dosing regimens based on the drug and the type and severity of adverse events or laboratory abnormalities are provided in Table 5-2 below. The dose modification instructions focus on the types of events most commonly attributed to each of the study agents. Required dose modifications and actions provided in Table 5-2 must be followed based on the type and severity of adverse avent. The recommendations provided in Table 5-2 comprise only guidelines; variations from these recommendations may be warranted based on an investigator's individual judgment in considering potential risks, benefits, and therapeutic alternatives available to each subject.

Consistent with Table 5-2, if a subject experiences an adverse event that is suspected to be related to study drug and requires a dose modification during the course of study therapy, then study drug administration should be held, as necessary, until the adverse event resolves or stabilizes to an acceptable degree Thereafter, study drug may be reinstituted, but the dose should be modified per(Table 5-1 and Table 5-2). If the adverse event occurs again, reinitiation of therapy may be attempted if the investigator feels that a second rechallenge is medically appropriate. If the subject cannot tolerate idelalisib at Dose Level -1 after 2 rechallenges, then the subject should be discontinued from study drug therapy unless continued therapy is discussed with the Gilead Sciences medical monitor.

After the study drug dose is reduced, the dose need not be re-escalated, even if there is minimal or no toxicity with the reduced dose. However, if the subject tolerates the lower dose level of study drug for ≥4 weeks then the dose level may be increased to the starting dose level (see Table 5-1) at the discretion of the investigator. Such re-escalation may be particularly warranted if further evaluation reveals that the adverse event that led to the dose reduction was not study-drug-related. The starting dose level should not intentionally be exceeded in this study.

Whenever possible, any dose adjustment of study drug should be discussed between the investigator and the Gilead Sciences medical monitor prior to implementation. To implement either a dose reduction or a dose reescalation, the investigator/study staff member will call the IWRS, enter the subject number, and inform the IWRS of the need for dose titration. The IWRS will provide details regarding the study drug to be dispensed to the subject. The appropriate clinic staff should instruct the subject/caregiver about the change in dose.

Recommendations for dose modification based on the type and severity of adverse events or laboratory abnormalities are provided in Table 5-2 below.

Table 5-2. Recommendations and Requirements for Study Drug Dose Modifications Based on Type and Severity of Treatment-Related Adverse Events or Laboratory Abnormalities

	Recommendation		
NCI CTCAE Grade ^a	Idelalisib		
HEMATOLOGICAL ADVERSE EVENTS			
Neutropenia			
Grade ≤2 neutropenia	Recommended Action: Maintain current dose level and schedule.		
Grade ≤3 neutropenia	Required Action: Blood counts should be monitored at least weekly until ANC Grade 2. Recommended Action: Maintain current idelalisib dose level and schedule.		
Grade 4 neutropenia (or occurrence of neutropenic fever or infection)	Required Action: Withhold idelalisib. Required Action: Monitor blood counts at least weekly until ANC Grade 2 Recommended Action: May resume idelalisib at lower dose level at investigator discretion. Neutropenia should be managed according to established clinical guidelines.		
Thrombocytopenia			
Grade ≤3	Recommended Action: Maintain current dose level and schedule.		
Grade 4	Required Action: Withhold idelalisib for bruising or bleeding until Grade ≤3. Recommended Action: May resume idelalisib at initial or lower dose level at investigator discretion.		
NON-HEMATOLOGI	CAL ADVERSE EVENTS		
Rash			
Grade ≤1	Recommended Action: Maintain current dose level and schedule.		
Grade 2	Recommended Action: Maintain current dose level and schedule.		

	Recommendation		
NCI CTCAE Grade ^a	Idelalisib		
Grade ≥3	Required Action: Withhold idelalisib until Grade ≤1. Recommended Action: Resume at lower dose level or discontinue idelalisib at investigator discretion.		
Stevens-Johnson Syndi	Stevens-Johnson Syndrome (SJS)/Toxic Epidermal Necrolysis (TEN)		
Any Grade	Required Action: Discontinue idelalisib. Interrupt coadministered medications potentially associated with SJS/TEN. Institute treatment per institutional standards.		
Gastrointestinal Inflammation/Diarrhea			
Grade ≤1	Required Action: Obtain history of onset and duration of diarrhea, including description, number of stools, stool composition (e.g., watery, bloody, nocturnal), travel history, dietary changes and a medication review to identify possible diarrheogenic agents.		
	Required Action: Perform physical examination including assessment for fever, dizziness, abdominal pain/cramping, and weakness (e.g., evaluate for sepsis, bowel obstruction, dehydration).		
	Recommended Action: Provide anti-diarrheal (eg, loperamide) and maintain current idelalisib dose level and schedule.		
Grade 2 diarrhea or colitis (unless clinical diagnosis is established from medical history and physical examination)	Required Action: Obtain history of onset and duration of diarrhea, including description, number of stools, and stool composition (e.g., watery, bloody, nocturnal), travel history, dietary changes and a medication review to identify possible diarrheogenic agents.		
	Required Action: Perform physical examination including assessment for fever, dizziness, abdominal pain/cramping, and weakness (e.g., evaluate for sepsis, bowel obstruction, dehydration).		
	Required Action: For Grade 2 colitis or diarrhea (unless clinical diagnosis is established from medical history and physical examination), perform stool culture for routine pathogens (Salmonella, Shigella, Campylobacter species, Clostridium difficile toxin, Rotavirus, Cytomegalovirus, Adenovirus), ova and parasites (Cryptosporidium parvum, Isospora belli, Enterocytozoon bieneusi, Septata intestinalis, Strongyloides, Microsporidia, Entamoeba histolytica, Cyclospora), and Giardia antigen.		
	Recommended Action: For persistent Grade 2 colitis or diarrhea without clear etiology (clostridium difficile enterocolitis), endoscopy with biopsy ^b is strongly recommended to assess by immunohistochemistry (IHC) and PCR for CMV, Adenovirus. (Optional: If ileal biopsy is performed, consider Acid Fast Bacillus staining.)		
	Recommended Action: Provide anti-diarrheal (eg, loperamide). Consider addition of anti- inflammatory agent (eg, sulfasalazine, budesonide). Maintain current idelalisib dose level and schedule.		

	Recommendation		
NCI CTCAE Grade ^a	Idelalisib		
Grade ≥ 3 diarrhea or colitis or persistent grade 2 diarrhea or colitis without clear etiology	Required Action: Withhold idelalisib.		
	Required Action: Obtain history of onset and duration of diarrhea, including description, number of stools, stool composition (e.g., watery, bloody, nocturnal), travel history, dietary changes and a medication review to identify possible diarrheogenic agents.		
	Required Action: Perform physical examination including assessment for fever, dizziness, abdominal pain/cramping, and weakness (e.g., evaluate for sepsis, bowel obstruction, dehydration).		
	Required Action: For Grade 3 colitis or diarrhea (unless clinical diagnosis is established from medical history and physical examination), perform stool culture for routine pathogens (Salmonella, Shigella, Campylobacter species, Clostridium difficile toxin, Rotavirus, Cytomegalovirus, Adenovirus), ova and parasites (Cryptosporidium parvum, Isospora belli, Enterocytozoon bieneusi, Septata intestinalis, Strongyloides, Microsporidia, Entamoeba histolytica, Cyclospora), and Giardia antigen.		
	Recommended Action: For Grade 3 colitis or diarrhea without clear etiology (eg, clostridium difficile enterocolitis), endoscopy with biopsy ^b isstrongly recommended to assess by immunohistochemistry (IHC) and PCR for CMV, Adenovirus (Optional: If ileal biopsy is performed, consider Acid Fast Bacillus staining.)		
	Recommended Action: At Grade ≤1, may resume idelalisib at lower dose level or discontinue at investigator discretion.		
	Recommended Action: Provide anti-diarrheal (eg, loperamide) and/or addition of anti-inflammatory agent (eg, sulfasalazine, budesonide).		
Hepatic Adverse Event	s (elevations in ALT, AST, or bilirubin)		
Grade ≤1 (ALT/AST≤3xULN) (Bilirubin≤1.5xULN)	Recommended Action: Maintain current dose level and schedule.		
Grade 2 (ALT/AST>3-5xULN) (Bilirubin>1.5- ≤3xULN)	Recommended Action: Monitor ALT, AST, ALP, and bilirubin at least 1x per week until all abnormalities are Grade ≤ 1; thereafter maintain current dose level.		
Grade 3 (ALT/AST>5-20xUL N) (Bilirubin>3-10xULN)	Recommended Action: Withhold idelalisib. Monitor ALT, AST, ALP, and bilirubin at least 1x per week until all abnormalities are Grade ≤1.		
	Recommended Action: If bilirubin abnormality was Grade <3, resume idelalisib at same dose level. If bilirubin abnormality was Grade >3, resume at lower dose level.		
	Required Action: Withhold idelalisib.		
Grade 4 (ALT/AST>20xULN)	Required Action: Monitor ALT, AST, ALP, and bilirubin at least 1x per week until all abnormalities are Grade ≤1.		
(AL1/AS1>20XULN) (Bilirubin>10xULN)	Required Action: If bilirubin abnormality was Grade 4, discontinue idelalisib.		
,	Required Action: If bilirubin abnormality was Grade <4, if drug is restarted then resume idelalisib at lower dose level.		

	Recommendation		
NCI CTCAE Grade ^a	Idelalisib		
Pneumonitis (with new o	Pneumonitis (with new onset or worsening baseline dyspnea, cough, or hypoxia without obvious infectious cause)		
Grade 1 (asymptomatic)	Required Action: Withhold idelalisib until resolution to baseline. May resume at lower dose level or discontinue idelalisib at investigator discretion.		
Grade ≥ 2	Required Action: Discontinue idelalisib permanently in subjects with any severity of symptomatic pneumonitis and institute therapy as clinically appropriate.		
Pneumocystis jirovecci pneumonia (PJP)			
Any Grade	Required Action: Discontinue idelalisib		
Organizing Pneumonia			
Any Grade	Required Action: Discontinue idelalisib permanently		
Unequivocal CMV infe	ction ^c		
Any Grade	Required Action: Interrupt idelalisib upon unequivocal clinical or laboratory evidence of CMV infection.		
	Required Action: Treat according to established clinical guidelines.		
	Required Action: If the benefits of resuming idelalisib are judged to outweigh the risks, consideration should be given to administering pre-emptive CMV therapy.		
Other Nonhematological Adverse Events			
Grade ≤2	Recommended Action: Maintain current dose level and schedule.		
Grade ≥3	Recommended Action: Withhold idelalisib until Grade ≤1. May resume idelalisib at initial or lower dose level or discontinue idelalisib at investigator discretion.		

a CTCAE, Version 4.03.

Abbreviations: ALP=alkaline phosphatase, ALT=alanine aminotransferase, AST= aspartate aminotransferase, CTCAE=Common Terminology Criteria for Adverse Events, CMV=cytomegalovirus, G-CSF=granulocyte colony-stimulating factor, NCI=National Cancer Institute, ULN=upper limit of normal

5.4. Evaluation, Intervention, and Drug Discontinuation for Specific Adverse Events or Conditions

